### **10.3 Responsibilities of the investigator and IRB/IEC**

Before initiating a trial, the investigator/institution must obtain approval/favorable opinion from the Institutional Review Board/Independent Ethics Committee (IRB/IEC) for the trial protocol, written informed consent form, consent form updates, subject recruitment procedures (e.g., advertisements) and any other written information to be provided to subjects. Prior to study start, the investigator is required to sign a protocol signature page confirming his/her agreement to conduct the study in accordance with these documents and all of the instructions and procedures found in this protocol and to give access to all relevant data and records to Novartis monitors, auditors, Novartis Quality Assurance representatives, designated agents of Novartis, IRBs/IECs, and regulatory authorities as required. If an inspection of the clinical site is requested by a regulatory authority, the investigator must inform Novartis immediately that this request has been made.

### **10.4 Publication of study protocol and results**

The key design elements of this protocol will be posted in a publicly accessible database such as [clinicaltrials.gov](http://clinicaltrials.gov). In addition, upon study completion and finalization of the study report the results of this trial will be either submitted for publication and/or posted in a publicly accessible database of clinical trial results.

### **10.5 Quality Control and Quality Assurance**

Novartis maintains a robust Quality Management (QM) system that includes all activities involved in quality assurance and quality control, including the assignment of roles and responsibilities, the reporting of results, and the documentation of actions and escalation of issues identified during the review of quality metrics, incidents, audits and inspections.

Audits of investigator sites, vendors, and Novartis systems are performed by Novartis Pharma Auditing and Compliance Quality Assurance, a group independent from those involved in conducting, monitoring or performing quality control of the clinical trial. The clinical audit process uses a knowledge/risk based approach.

Audits are conducted to assess GCP compliance with global and local regulatory requirements, protocols and internal Standard Operating Procedures (SOPs), and are performed according to written Novartis processes.

## 11 Protocol adherence

This protocol defines the study objectives, the study procedures and the data to be collected on study participants. Additional assessments required to ensure safety of subjects should be administered as deemed necessary on a case by case basis. Under no circumstances is an investigator allowed to collect additional data or conduct any additional procedures for any research related purpose involving any investigational drugs under the protocol.

Investigators ascertain they will apply due diligence to avoid protocol deviations. If an investigator feels a protocol deviation would improve the conduct of the study this must be considered a protocol amendment, and unless such an amendment is agreed upon by Novartis and approved by the IRB/IEC and health authorities, where required, it cannot be implemented.

### 11.1 Protocol amendments

Any change or addition to the protocol can only be made in a written protocol amendment that must be approved by Novartis, health authorities where required, and the IRB/IEC prior to implementation. Only amendments that are intended to eliminate an apparent immediate hazard to subjects may be implemented immediately provided the health authorities are subsequently notified by protocol amendment and the reviewing IRB/IEC is notified. Notwithstanding the need for approval of formal protocol amendments, the investigator is expected to take any immediate action required for the safety of any subject included in this study, even if this action represents a deviation from the protocol. In such cases, the reporting requirements identified in [Section 7](#) Safety Monitoring must be followed.

## 13 Appendices

### 13.1 Appendix 1: Clinically notable laboratory values and vital signs

The following criteria will be used to define expanded limits and notable abnormalities of key laboratory tests. Notable values for blood pressure and pulse are presented in [Section 6.5.2](#).

No specific action is pre-defined within this protocol to respond to specific abnormal laboratory values, as it will be decided by the investigator whether and which specific action needs to be taken to respond to any abnormal values, taking into account the overall status of the subject.

#### Liver Function and Related Variables

- Alanine transaminase (ALT) (SGPT): > 3 x Upper Limit of Normal (ULN)
- Aspartate transaminase (AST) (SGOT): > 3 x ULN
- Total bilirubin: > 2 x ULN
- Alkaline phosphatase: > 2.5 x ULN

#### Hematology Variables

- Hemoglobin:  $\geq 20$  g/dL decrease from baseline
- Platelet count: < Lower Limit of Normal (LLN)
- White blood cell count: < 0.8 x LLN
- Neutrophils: < 0.9 x LLN
- Eosinophils: > 1.1 x ULN
- Lymphocytes: > 1.1 x ULN

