#### **6.5.4 Laboratory evaluations**

A central laboratory will be used for analysis of all specimens listed below, unless noted otherwise. Details on the collections, shipment of samples and reporting of results by the central laboratory are provided to investigators in the laboratory manual. Refer to the Laboratory Manual for identification of laboratory reference range values and the schema for notification of site staff and Novartis for out of range values.

Subjects should avoid smoking within the hour preceding the blood draws.

[Appendix 1](#) shows the extended laboratory ranges that are considered clinically notable.

No specific action is pre-defined within this protocol to respond to specific abnormal laboratory values, as it will be decided by the investigator whether and which specific action needs to be taken to respond to any abnormal values, taking into account the overall status of the subject.

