## **7 Safety monitoring**

### **7.1 Adverse events**

An adverse event (AE) is any untoward medical occurrence (e.g., any unfavorable and unintended sign [including abnormal laboratory findings], symptom or disease) in a subject or clinical investigation subject after providing written informed consent for participation in the

study until the end of study visit. Therefore, an AE may or may not be temporally or causally associated with the use of a medicinal (investigational) product.

In addition, all reports of intentional misuse and abuse of the product are also considered an adverse event irrespective if a clinical event has occurred.

The occurrence of adverse events must be sought by non-directive questioning of the subject at each visit during the study. Adverse events also may be detected when they are volunteered by the subject during or between visits or through physical examination findings, laboratory test findings, or other assessments.

Abnormal laboratory values or test results constitute adverse events only if they fulfill at least one of the following criteria:

- they induce clinical signs or symptoms,
- they are considered clinically significant,
- they require therapy.

Clinically significant abnormal laboratory values or test results must be identified through a review of values outside of normal ranges/clinically notable ranges, significant changes from baseline or the previous visit, or values which are considered to be non-typical in subject with underlying disease. Investigators have the responsibility for managing the safety of individual subject and identifying adverse events. Alert ranges for laboratory and other test abnormalities are included in [Appendix 1](#).

Adverse events must be recorded in the appropriate CRF capturing Adverse Events under the signs, symptoms or diagnosis associated with them, accompanied by the following information:

- the severity grade
  - mild: usually transient in nature and generally not interfering with normal activities
  - moderate: sufficiently discomforting to interfere with normal activities
  - severe: prevents normal activities
- its relationship to the study treatment (suspected: Yes / No)
- its duration (start and end dates) or if the event is ongoing an outcome of not recovered/not resolved must be reported.
- whether it constitutes a serious adverse event (SAE - See [Section 7.2](#) for definition of SAE) and which seriousness criteria have been met.

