ALT or AST & TBL & ALP	ALT or AST >3xULN & TBL >2xULN & ALP <2xULN (Potential Hy's Law) Note: elevated ALP may suggest obstruction as a consequence of gall bladder or bile duct disease; ALP may also be increased in malignancy. FDA therefore terms Hy's Law cases as indicators of pure hepatocellular injury . This does not mean that cases of ALT or AST >3xULN & TBL >2xULN & ALP >2xULN may not result in severe DILI. ALT or AST >3xULN & TBL >2xULN & ALP <2xULN (Potential Hy's Law) or reported Hy's Law case Note: "Hy's Law case" is a lower level term in MedDRA (10070546) and may be reported as AE.

For a combined criterion to be fulfilled, all conditions have to be fulfilled on the same visit. The criteria are not mutually exclusive, e.g., a subject with ALT = 6.42xULN is counted for ALT >3xULN and ALT >5xULN.

Individual subject data listings will be provided for subjects with notably abnormal laboratory values (reference to Protocol Amendment 1, Appendix 1) and newly occurring or worsening abnormal laboratory data by CTC grades. Data of subjects with newly occurring liver enzyme abnormalities will be listed in an additional listing.

Fasting laboratory tests including fasting plasma glucose and fasting lipids will be evaluated only at screening. No analysis will be done for these measurements.

For urinalysis, standard dipstick measurements for specific gravity, protein, glucose, pH, blood, urine blood (non-hemolyzed), urine blood (hemolyzed), bilirubin, ketones, WBC will be done at screening. No analysis will be done for these measurements.

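### Protocol Appendix 1 sets the notable-haemoglobin criterion at a fall of at least 20 g/dL (200 g/L), which no subject with a baseline below 200 g/L can meet

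*Protocol*

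**What the plan says.** Under Hematology Variables, Protocol Appendix 1 (section 13.1) gives the haemoglobin entry as at least 20 "g/dL decrease from baseline". The appendix states its own role: "The following criteria will be used to define expanded limits and notable abnormalities of key laboratory tests". Two other protocol sections rely on it. Section 6.5.4 says that Appendix 1 "shows the extended laboratory ranges that are considered clinically notable", and section 7.1, on identifying adverse events, says "Alert ranges for laboratory and other test abnormalities are included in" that appendix.

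SAP 2.8.4 also uses it: "Individual subject data listings will be provided for subjects with notably abnormal laboratory values (reference to Protocol Amendment 1, Appendix 1". SAP Table 2-7 grades haemoglobin separately by CTCAE, in g/L, with cut-points at the lower limit of normal (LLN), 100 g/L and 80 g/L.

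The appendix also limits what follows from a notable value: "No specific action is pre-defined within this protocol to respond to specific abnormal laboratory values". The decision is left to the investigator.

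**The concern.** A drop of 20 g/dL is of the order of a subject's whole haemoglobin concentration, not a change in it. The SAP's own scale shows this: its lowest numerical cut-point is 80 g/L, while the Appendix 1 entry asks for a fall of 200 g/L.

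The other laboratory entries in Appendix 1 are multiples of the upper or lower limit of normal, or the limit itself. Haemoglobin is the only one defined purely by change from baseline, and it has no absolute limit there to fall back on. If the change criterion cannot be met, Appendix 1 has no working haemoglobin criterion for subjects with a baseline below 200 g/L. A trial comparing the safety of a higher-exposure regimen with the approved one would then report notable laboratory values under a definition that cannot pick up a fall in haemoglobin in those subjects.

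**Working it through.** **Inputs**
- Threshold: fall from baseline of at least 20 g/dL (Protocol Appendix 1, Hematology Variables).
- SAP scale: g/L, with numerical cut-points at 100 and 80 (SAP Table 2-7).
- Baseline haemoglobin: not given in either document. The values below are assumed, for illustration only; the bound itself does not depend on them.

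The threshold is a stated limit, not a derived figure, so there is no calculation in the plan to reproduce.

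**Step 1, unit.** 20 g/dL × 10 = 200 g/L.

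**Step 2, feasibility.** The criterion is baseline − value ≥ 200 g/L. Because value ≥ 0, the largest possible fall equals the baseline. The criterion therefore requires baseline ≥ 200 g/L.

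**Step 3, value needed.** A qualifying result must be no higher than baseline − 200 g/L:

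| Assumed baseline (g/L) | Qualifying value must be at most (g/L) | Attainable? |
|---|---|---|
| 120 | −80 | No |
| 140 | −60 | No |
| 160 | −40 | No |
| 180 | −20 | No |
| 199 | −1 | No |
| 200 | 0 | Formally, at 0 only |
| 210 | 10 | Formally |
| 220 | 20 | Formally |

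**Step 4, comparison with the SAP's grading.** From an assumed baseline of 140 g/L, a drop to 79 g/L is below 80 g/L and so CTCAE grade 3. The fall is 140 − 79 = 61 g/L, and Appendix 1 would not call it notable. For a 200 g/L fall to leave a subject above 80 g/L, the baseline would have to exceed 80 + 200 = 280 g/L.

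**Step 5, what else would catch a fall.** CTCAE grades and out-of-range flags depend on crossing an absolute limit, so a large fall that stays within the normal range triggers neither, and the shift table shows normal to normal. Change-from-baseline summaries in SAP 2.8.4, and the maximum-decrease analysis in Protocol 9.5.2, are at group level. The full laboratory listing contains the values but applies no rule to the size of a fall. Investigator review under Protocol 7.1 covers "significant changes from baseline or the previous visit", but by judgement and without a number.

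**The case against.** The strongest objection is to the certainty. The text checked here was read from PDF, and the haemoglobin line carries a symbol that was converted as a formula, whereas its neighbours came through as plain text. The intact decimals nearby (0.8, 0.9, 1.1, 2.5) are therefore only modest reassurance, and a dropped decimal point or altered unit on the source page cannot be excluded. This stands as a reason to look at the page first. Nothing in the line itself shows damage.

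The second objection is consequence. No action follows from a notable value, investigators must review meaningful changes whatever the appendix says, and the SAP lists all laboratory data and provides CTCAE tables, shift tables and out-of-range flags. No estimate, test or eligibility rule uses the line. All of this is right and keeps the severity low.

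Third, the practical reach is uncertain. The SAP cites Appendix 1 of Protocol Amendment 1, and the documents do not show whether the supplied protocol is that version. Section 6.5.4 places "the schema for notification of site staff and Novartis for out of range values" in the Laboratory Manual, which is not among the documents, so any effect on site alerts is unknown. Both limits stand. Neither changes the fact that the criterion, as printed, is unattainable from any baseline below 200 g/L.

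Finally, the criterion is formally attainable at a baseline of 200 g/L or more. That is true, but it then requires a result at or near zero (Step 3).

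**Conclusion.** The concern holds on the text as supplied: the criterion cannot be met from any baseline below 200 g/L, and no other section of either document corrects it. The bound follows from the printed number, the unit and the fact that a concentration cannot be negative; no assumed baseline is needed.

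The point is minor. What fails is the single numerical rule that would identify individual subjects by the size of a haemoglobin fall, and with it the haemoglobin part of the SAP 2.8.4 notable-values listing if the supplied appendix is the cited version. How many subjects would be missed cannot be quantified. The conclusion is conditional on the source page reading the same as the extracted text.

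**What to change.** 1. Check the Appendix 1 source page, and confirm whether it is the version that SAP 2.8.4 cites.
2. If the line stands as printed, the sponsor should correct the value or the unit so that the criterion is attainable. The documents do not show which of the two is wrong, and no threshold is proposed here.
3. State the corrected criterion in g/L, or give both units, so that it reads directly against SAP Table 2-7. This is for convenience, since the two units convert exactly.
4. Apply the corrected criterion in the SAP 2.8.4 listing, and confirm that the Laboratory Manual does not carry the same entry.

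The cost is one line in the protocol appendix. No new data are needed, and no summary table or hypothesis test changes.

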## 13.2 Appendix 2: Liver event and Laboratory trigger Definitions and Follow-up Requirements

**Table 13-1 Liver Event and Laboratory Trigger Definitions**

	Definition/ threshold
LIVER LABORATORY TRIGGERS	
 
• <math>3 \times \text{ULN} < \text{ALT} / \text{AST} \leq 5 \times \text{ULN}</math>
 
• <math>1.5 \times \text{ULN} < \text{TBL} \leq 2 \times \text{ULN}</math>
 

LIVER EVENTS	
 
• <math>\text{ALT or AST} > 5 \times \text{ULN}</math>
 
• <math>\text{ALP} > 2 \times \text{ULN}</math> (in the absence of known bone pathology)
 
• <math>\text{TBL} > 2 \times \text{ULN}</math> (in the absence of known Gilbert syndrome)
 
• <math>\text{ALT or AST} > 3 \times \text{ULN}</math> and <math>\text{INR} > 1.5</math>
 
• Potential Hy's Law cases (defined as <math>\text{ALT or AST} > 3 \times \text{ULN}</math> and <math>\text{TBL} > 2 \times \text{ULN}</math> [mainly conjugated fraction] without notable increase in <math>\text{ALP}</math> to <math>> 2 \times \text{ULN}</math>)
 
• Any clinical event of jaundice (or equivalent term)
 
• <math>\text{ALT or AST} > 3 \times \text{ULN}</math> accompanied by (general) malaise, fatigue, abdominal pain, nausea, or vomiting, or rash with eosinophilia
 
• Any adverse event potentially indicative of a liver toxicity*
 

\*These events cover the following: hepatic failure, fibrosis and cirrhosis, and other liver damage-related conditions; the non-infectious hepatitis; the benign, malignant and unspecified liver neoplasms  
TBL: total bilirubin; ULN: upper limit of normal; INR: international normalized ratio

**Table 13-2 Follow-up Requirements for Liver Events and Laboratory Triggers**

Criteria	Actions required	Follow-up monitoring
Potential Hy's Law case a	
 
• Discontinue the study treatment immediately
 
• Hospitalize, if clinically appropriate
 
• Establish causality
 
• Complete appropriate CRF to record the AE and any contributory factors
 
	ALT, AST, TBL, Alb, PT/INR, ALP and GGT until resolution c (frequency at investigator discretion)
ALT or AST		
$> 8 \times \text{ULN}$	
 
• Discontinue the study treatment immediately
 
• Hospitalize if clinically appropriate
 
• Establish causality
 
• Complete appropriate CRF to record the AE and any contributory factors
 
	ALT, AST, TBL, Alb, PT/INR, ALP and GGT until resolution c (frequency at investigator discretion)
$> 3 \times \text{ULN}$ and $\text{INR} > 1.5$	
 
• Discontinue the study treatment immediately
 
• Hospitalize, if clinically appropriate
 
• Establish causality
 
• Complete appropriate CRF to record the AE and any contributory factors
 
	ALT, AST, TBL, Alb, PT/INR, ALP and GGT until resolution c (frequency at investigator discretion)
$> 5$ to $\leq 8 \times \text{ULN}$	
 
• Repeat LFT within 48 hours
 
• If elevation persists, continue follow-up monitoring
 
• If elevation persists for more than 2 weeks, discontinue the study drug
 
	ALT, AST, TBL, Alb, PT/INR, ALP and GGT until resolution c (frequency at investigator discretion)

Criteria	Actions required	Follow-up monitoring
	
 
Establish causality
 
Complete appropriate CRF to record the AE and any contributory factors
 
	
> 3 × ULN accompanied by symptoms b	
 
Discontinue the study treatment immediately
 
Hospitalize if clinically appropriate
 
Establish causality
 
Complete appropriate CRF to record the AE and any contributory factors
 
	ALT, AST, TBL, Alb, PT/INR, ALP and GGT until resolution c (frequency at investigator discretion)
> 3 to ≤ 5 × ULN (patient is asymptomatic)	
 
Repeat LFT within the next week
 
If elevation is confirmed, initiate close observation of the patient
 
	Investigator discretion Monitor LFT within 1 to 4 weeks
ALP (isolated)		
> 2 × ULN (in the absence of known bone pathology)	
 
Repeat LFT within 48 hours
 
If elevation persists, establish causality
 
Complete appropriate CRF to record the AE and any contributory factors
 
	Investigator discretion Monitor LFT within 1 to 4 weeks or at next visit
TBL (isolated)		
> 2 × ULN (in the absence of known Gilbert syndrome)	
 
Repeat LFT within 48 hours
 
If elevation persists, discontinue the study drug immediately
 
Hospitalize if clinically appropriate
 
Establish causality
 
Complete appropriate CRF to record the AE and any contributory factors
 
	ALT, AST, TBL, Alb, PT/INR, ALP and GGT until resolution c (frequency at investigator discretion) Test for hemolysis (e.g., reticulocytes, haptoglobin, unconjugated [indirect] bilirubin)
> 1.5 to ≤ 2 × ULN (patient is asymptomatic)	
 
Repeat LFT within the next week
 
If elevation is confirmed, initiate close observation of the patient
 
	Investigator discretion Monitor LFT within 1 to 4 weeks or at next visit
Jaundice	
 
Discontinue the study treatment immediately
 
Hospitalize the patient
 
Establish causality
 
Complete appropriate CRF to record the AE and any contributory factors
 
	ALT, AST, TBL, Alb, PT/INR, ALP and GGT until resolution c (frequency at investigator discretion)
Any AE potentially indicative of a liver toxicity*	
 
Consider study treatment interruption or discontinuation
 
Hospitalization if clinically appropriate
 
Establish causality
 
Complete appropriate CRF to record the AE and any contributory factors
 
	Investigator discretion

aElevated ALT/AST > 3 × ULN and TBL > 2 × ULN but without notable increase in ALP to > 2 × ULN

b(General) malaise, fatigue, abdominal pain, nausea, or vomiting, or rash with eosinophilia

cResolution is defined as an outcome of one of the following: (1) return to baseline values, (2) stable values at three subsequent monitoring visits at least 2 weeks apart, (3) remain at elevated level after a maximum of 6 months, (4) liver transplantation, and (5) death.

MedDRA	Medical Dictionary for Drug Regulatory Affairs
NMQ	Novartis MedDRA Query
NovDTD	Novartis Drug and Therapy Dictionary
PASI	Psoriasis Area and Severity Index
PD	Protocol deviation
████	████████████████████
PT	Preferred Term
RMP	Risk Management Plan
SAS	Statistical analysis software
SAE	Serious adverse event
SOC	System Organ Class
TEAE	Treatment Emergent Adverse Event
ULN	Upper Limit of Normal
WBC	White blood cell

1 Introduction

Data will be analyzed by Novartis according to the data analysis section 9 of the study protocol which is available in [Appendix 16.1.1 of the CSR](#). Important information is given in the following sections and details are provided, as applicable, in [Appendix 16.1.9 of the CSR](#).

This document covers statistical and analytical plans for CAIN457A2324 study with reference to the study protocol and the project standard analysis plans [REDACTED].

1.1 Study design

This is a 52-week multicenter, randomized, double-blind, parallel-group trial in approximately 330 subjects with moderate to severe chronic plaque-type psoriasis of body weight 90 kg or higher at time of randomization.

The study consists of 4 periods: screening (up to 4 weeks), treatment period 1 (16 weeks), treatment period 2 (36 weeks), and follow-up (8 weeks).

Patients will be randomized using a 1:1 ratio to one of the following treatment groups at randomization (baseline) visit ([Figure 1-1](#)):

- Secukinumab 300 mg every 2 weeks
- Secukinumab 300 mg every 4 weeks

Patients who complete treatment period 1 will enter treatment period 2. For patients who discontinued study treatment prematurely before week 16 visit (EOT 1), an EOT 1 visit should be performed and then patients should enter follow-up period.

[figure not shown]
At week 16, patients will be assigned to the following treatment groups based on the randomization done at the randomization/baseline visit (details described later):

- Subjects from the 300 mg every 2 weeks group will remain on secukinumab 300 mg every 2 weeks until the end of treatment
- Subjects from the 300 mg every 4 weeks group:

- [REDACTED]
- [REDACTED]
- [REDACTED]
- [REDACTED]

Patients will complete the treatment period 2 at week 52. For all subjects who discontinue study treatment prematurely before Week 52 (EOT2), an EOT2 visit should be performed and then subjects should enter follow-up period.

Figure 1-1 Study design

Randomization process:

To mitigate the risk of randomization error at week 16, a single randomization for both treatment period 1 and treatment period 2 will be done both at randomization/baseline visit. This means there will not be a re-randomization happen at week 16. Patients will be randomized at baseline visit using a 2:1:1 ratio into one of the treatment groups below (Figure 1-2 Randomization Process).

[figure not shown]
- **AIN457 300mg Q2W** : secukinumab 300 mg every 2 weeks
- **AIN457 300mg Q4W**: secukinumab 300 mg every 4 weeks, subjects will continue on 300 mg every 4 weeks during treatment period 2 regardless their PASI 90 response status at Week 16.

[REDACTED]

[REDACTED]

[REDACTED]

Figure 1-2 Randomization Process

No randomization stratification applies to this trial.

The following study periods will be considered for analysis:

- **Screening period** (Screening to Randomization)
- **Treatment period 1** (Randomization to Week 16 pre-dose including follow-up visits (F4 and F8) for patients prematurely discontinued during treatment period 1)
- **Treatment period 2** (Week 16 dose to EOT2/Week 52 including follow-up visits (F4 and F8) for patients prematurely discontinued)
- **Entire treatment period** (Randomization to EOT 2/Week 52 including follow-up visits (F4 and F8) for patients prematurely discontinued)
- **Entire study period** (Randomization to EOS/F8 including follow-up visits (F4 and F8) for all patients)

All data will be presented for the final analysis.

